The Impact of Adjuvant Liquid Alginate on Endoscopic Ablation Therapy of Complicated Barrett's Esophagus: A Pilot Study

NCT03193216

Document Date: 12/05/2018

RESEARCH PLAN

PROTOCOL TITLE:

The Impact of Adjuvant Liquid Alginate on Endoscopic Ablation Therapy of Complicated Barrett's Esophagus: A Pilot Study

PRINCIPAL INVESTIGATOR:

- [name], MPH

CO-INVESTIGATORS:

- [name], [name], [name], [name], B. [name]

COLLABORATORS:

[name] Ph.D, [name], MS

Background

Barrett's esophagus (BE) is a pre-cancerous condition in the esophagus that results from constant acid exposure and is a precursor to esophageal adenocarcinoma (EAC). Surprisingly, EAC rates continue to rise despite efforts aimed at addressing BE. Patients with dysplastic BE are at increased risk for developing EAC and in high grade dysplasia (HGD), this risk can be as high as 6% per year. For these reasons, these patients are candidates for ablation therapy, either with cryotherapy, endoscopic mucosal resection (EMR), and/or radiofrequency ablation (RFA). In patients receiving ablative therapy, 3-5 treatments are typically required before there is resolution of all Barrett's epithelium while patients remain on twice daily proton pump therapy²⁹. A recent case study by the current authors demonstrated initial failed response of BE with HGD to RFA and subsequently cryotherapy. *Only* after initiation of a liquid alginate solution (Gaviscon Advance - UK formulation) was there a subsequent rapid and complete response to therapy. This case suggests that liquid alginate provided additional esophageal protection allowing mucosal healing and an overall enhanced response to treatment. This finding is mechanistically plausible given existing evidence demonstrating the carcinogenic properties of bile acids and injurious activity of pepsin in non-acid refluxate, and liquid alginate's unique ability to control these components and inhibit acid reflux^{1,2,5,6,7,8,10,16,18,21,25,26,34}. We feel further investigation is warranted in studying the role of adjunct liquid alginate solution in patients undergoing treatment for BE.

The ingredient of interest in is alginic acid (alginate), a polysaccharide found in the cell walls of brown algae. Alginates are unique in their ability to form a protective layer above gastric contents upon exposure to gastric acid, thus limiting exposure of esophageal epithelium to gastric acid, bile acid, pepsin, and other parts of the gastric contents. Concurrently, the bicarbonate in alginate-based solutions forms carbon dioxide in the presence of gastric acid, which converts the gel into foam which floats to the surface of the gastric contents. Hence, alginate solutions form "rafts" which provide a physical barrier to acid reflux, as well as a pH-neutral substitute which refluxes preferentially over gastric acid^{12,13,17}.

It is noteworthy that Gaviscon Advance, which is approved for over-the-counter use in Europe by the European Medicines Agency (EMA) but not FDA approved in the U.S., is qualitatively and quantitatively different from U.S. Gaviscon formulations in terms of alginate composition. Gaviscon Advance, but not American Gaviscon, has demonstrated superiority to placebo, non-inferiority to proton pump inhibitors (PPIs), and efficacy as add-on therapy in patients already on PPI with regard to relieving symptoms of GERD^{4,15,22}. Furthermore, only the UK version of dual action antacid (antacid with alginate) has been shown to be superior to antacids alone in reducing post-prandial esophageal acid exposure in GERD patients¹⁹. Finally, as [name] et al. have demonstrated in a comparison of raft characteristics between a range of alginate/antacid formulations, Gaviscon Advance forms alginate rafts more quickly than other

formulations (most notably U.S. Gaviscon formulations), and these rafts are more coherent, have more complete flotation, and are of greater resiliency, weight, strength and volume than regular and extra strength Gaviscon (USA)³⁰.

Hypotheses & Specific Aims

H1 (primary): Adjuvant treatment with liquid alginate solution in addition to proton pump inhibitor (PPI) therapy will result in complete endoscopic eradication of complicated Barrett's esophagus (BE) more rapidly than endoscopic treatment on PPI therapy alone.

H2 (secondary): Adjuvant treatment with liquid alginate solution in addition to PPI therapy will result in fewer endoscopic treatment sessions necessary to achieve complete eradication of complicated BE compared to treatment with PPI alone.

SA 1 (primary): Eradication rate at one year will be compared between current recruits (i.e. study patients on adjuvant liquid alginate) and historical controls. Patients will be matched by type of therapy, and to the best of our ability, length of Barrett's.

SA2 (secondary): To compare the duration of treatment required to achieve complete endoscopic eradication of BE in patients treated with the combination of PPI and liquid alginate solution vs. those treated with PPI alone.

SA 3 (tertiary): To compare the number of treatment sessions required to achieve endoscopic eradication of BE in patients treated with the combination of PPI and liquid alginate solution vs. those treated with PPI alone.

Study Design

This is a pilot prospective cohort study at a single tertiary care center. Patients with BE and proven dysplasia (high or low grade) or risk of other abnormality presenting to our tertiary care center interested in endoscopic treatment will be asked to participate in the study. Participation will involve taking 10 mL of Gaviscon Advance four times daily along with twice daily PPI during the treatment duration. The control group will be a historical cohort of Barrett's esophagus patients treated in the last 5 years by the same endoscopists using similar approaches—these are patients who were prescribed twice daily PPI therapy alone during treatment.

Eligibility Criteria

Patients who are already scheduled for treatment of their dysplastic Barrett's esophagus or risk of other abnormality who are planning to undergo EMR, or ablation therapy with cryotherapy (spray or balloon) and/or RFA (with or without EMR) will be eligible for enrollment.

Inclusion criteria (all must be present):

- (1) Age ≥ 18
- (2) Patients already previously scheduled for treatment of complicated Barrett's esophagus
- (3) Long Segment Barrett's ($>3\text{cm}$)

Exclusion criteria:

- (1) Moderate to severe renal impairment, as defined by eGFR < 60 for 2 consecutive readings
- (2) Lack of capacity for decision-making
- (3) Allergy to hydroxybenzoates

- (4) Patients with uncontrolled hypertension or decompensated heart failure
- (5) Pregnancy- patients of child-bearing potential will be tested.
- (6) Patients with elevated calcium or potassium on screening laboratory testing (labs completed within the last month)

Enrollment

Eligible patients who provide informed consent will be included in this prospective study and asked to take the alginate solution in addition to their twice daily PPI therapy. If patients are on concurrent H2 blocker therapy, this will be stopped after enrollment in the study. Subjects will be primarily recruited in the office setting, following decision to undergo ablation therapy. Upon the start of ablation therapy, patients will start taking 10ml of Gaviscon Advance 30 minutes after every meal and at bedtime (4 daily doses, after breakfast, lunch, dinner and before bed). This will begin on the day of the first endoscopy, after the ablation treatment. PPI therapy will continue as previously prescribed.

Endoscopic treatment

Standard guidelines will be followed for patients undergoing EMR, RFA or cryotherapy or RFA, up to 8-10 cm can be treated during one session and sessions are scheduled every 10-12 weeks. For cryotherapy, approximately the same area can be treated (8-10cm) during one session, and sessions are scheduled every 8-10 weeks. When initial EMR is performed, follow-up endoscopic ablative therapy will be scheduled approximately 8 weeks later. The decision of which therapy to implement depends largely on anatomy and patient preference and will be determined by the endoscopists involved in the study—[name] (PI), [name], or [name]. Furthermore, all decisions pertaining to the need for repeat procedures to address inadequate treatment or incomplete tissue sampling, or the decision to refer for the alternate procedure, will be dictated by the above endoscopists. As mentioned previously, number of sessions to achieve complete eradication of Barrett's varies by length, but on average can take anywhere from 3-5 sessions, depending on initial length of BE as well as existence and size of hiatal hernia³¹.

Follow-up Assessments

All enrolled subjects will be followed until resolution of Barrett's is achieved, as confirmed by biopsy and endoscopic visualization. A measurement system referred to as the Prague classification³² will be used to document areas of the esophagus with Barrett's and to assess improvement from one endoscopy to another. This system allows the endoscopist to record the area of Barrett's involved by describing the area involved that is circumferential in nature and the area that is patchy. Decrease in surface area involved will help guide the aim for the study. During treatment sessions, pertinent clinical and endoscopic data will be collected (see Appendix A). Immediately prior to each treatment visit, an office visit will take place at the MUSC Gastroenterology endoscopy/outpatient clinic with study personnel including the PI, research coordinator, and/or fellow/resident participating in the study, which will serve to collect data regarding blood pressure, surveillance serum chemistries, treatment experience, adverse events to the drug, or any other issues (see Appendix B). Adherence to the medication regimen will be done by asking patients to bring in all used and unused bottles. IDS will assist in calculating how much drug has been taken and this data will be recorded at each visit. These data will then be entered into a coded RedCap database. At approximately six week intervals, the study research coordinator will call to verify medication regimen adherence as well as any adverse events associated with the study drug.

From the time of biopsy proven remission, patient medical records will be reviewed for up to 2 years to evaluate recurrences rates.

Outcomes

Eradication rate of intestinal metaplasia (complete remission of intestinal metaplasia – CRIM) at one year will be the primary outcome. The length of time to eradication and the number of endoscopic procedures required for CRIM will be the secondary and tertiary outcomes. CRIM will be defined as visual endoscopic evidence of neo-squamous epithelium occupying previous area of Barrett's epithelium combined with biopsies showing normal squamous esophageal epithelium without intestinal metaplasia.

When endoscopic eradication is observed, tissue biopsies of the GEJ and previously treated epithelium will be taken according to the Seattle protocol which recommends biopsies in a four quadrant fashion every 1 cm for a history of high grade dysplasia and every 2 cm for a history of low grade dysplasia³³. For areas of mucosal irregularity, targeted biopsies will also be taken. Patients who have achieved eradication but on subsequent biopsies have recurrence of Barrett's will undergo ablation treatment again until eradication is once again achieved. The presence of dysplasia on any one specimen will prohibit a claim of eradication.

The endoscopic footage from each study procedure will be video recorded. After quality assurance of the footage and removal of all identifiers, videos may be reviewed by a blinded and independent panel to confirm potentially subjective outcomes, such as the presence and extent of residual Barrett's epithelium. De-identified videos may be distributed to reviewers electronically, or may be reviewed during in-person sessions.

Adverse events related to the study drug will be defined according to standard consensus guideline documents published in the gastroenterology literature.

Sample Size Calculation and Statistical Consideration

We will compare the time to complete BE eradication/resolution (CRIM) between the prospective and historical cohorts using Kaplan-Meier time-to-event (time-to-CR) curves. The historical data maintained by the PI have n= 32 patients treated under similar conditions (e.g. facility, physicians) as the study patients who will be prospectively treated. As the purpose of this pilot study is to estimate the time to CRIM with the addition of liquid alginate for approximately 20 enrolled patients, no hypothesis testing will be performed to compare the distributions (hence, no power calculation). Comparisons will be descriptive only. Time-to-CR is assumed to be exponentially distributed and we will use the maximum likelihood estimate to estimate the rate parameter for each cohort. Patients who do not reach CR by the end of the study will be censored at that time. The difference in the rate parameter between cohorts will be calculated with a 95% confidence interval. Median time to CR will be estimated based on these parameters. Median time to CR under current treatments is about 22 months²⁷. If median time to CR with liquid alginate solution is sufficiently improved (e.g. to < 18 months), we will have high-quality pilot data with which to estimate a sample size for a more definitive randomized trial. Additionally, we will tabulate the number of treatments required to achieve CR and compare descriptively between cohorts as a secondary endpoint. Analyses above will also be stratified according to important covariates, such as disease grade and type of treatment (RFA or Cryotherapy).

Data Collection, Management, and Quality Control Procedures

Data entry will occur through RedCap, which will allow for study data to be directly entered into the database by the site via a secure internet connection. In addition to use of passwords and other security measures, all documents containing identifying information on individuals or physicians are considered confidential materials and will be safeguarded to the greatest possible extent. No information identifying a specific person, hospital, or physician will be released to or discussed with anyone other than study staff members. Appendix C shows the data points that will be collected from both the clinical and endoscopic visits.

Study Sites and Timeline

This is a single center study which will be conducted solely at MUSC. Patients will be monitored with a telephone call every six weeks as mentioned above and they will be provided with information to get in touch with the study team if they have problems between their visits.. Enrollment will be ongoing until an adequate number of subjects have been recruited. Thus, we anticipate that the study can be completed within 2 years.

Monitoring

All study data will be monitored routinely for completeness, timeliness, and consistency by the project manager. Data accuracy will be verified on a quarterly basis by the project manager and principal investigator. Due to a relatively small “n”, all subjects’ data will be reviewed. Discovered discrepancies between recorded study data and information found in medical records will be addressed through discussions between the PI and research coordinator. Subjects may be withdrawn from the study if they are lost to follow up, or if they endorse lack of compliance with liquid alginate solution and/or PPI therapy.

Safety

Gaviscon Advance is considered a very safe medication with a very mild side effect profile. It is widely available in the UK but not available in the US. An FDA IND application has been filed for its use for this study. Gaviscon Advance will be purchased directly from the pharmaceutical company, Reckitt Benckiser. Each 10 mL oral suspension contains 1g sodium alginate and 200 mg potassium hydrogen carbonate (active ingredients). The formulation also contains calcium carbonate, carbomer, sodium saccharin, sodium hydroxide, and so any patients who have been advised to restrict their diet from any of these substances should consult a doctor before taking Gaviscon Advance. Patients who suffer for have suffered from significant kidney or heart disease should speak with a physician before taking Gaviscon. Finally, the formulation includes methyl and propyl para-hydroxybenzoates which may cause allergic reactions (less than 1 in 10,000 patients), including skin rash, itching, difficulty breathing, dizziness, or swelling. Overdosing of the medication may cause bloating. Please see summary of product characteristics – Appendix D).

Any adverse event, either related to Gaviscon Advance or not, will be recorded in pre-treatment clinic and/or treatment visits, and will be evaluated by a safety review committee (see below).

Safety Review Committee

A safety review committee will be assembled for this clinical study. This committee will be composed of 3 persons who are not study investigators. The overall goals of the committee will include the following: 1) identify unacceptably slow rates of accrual, 2) identify high rates of ineligibility, 3) identify protocol violations that suggest clarification of changes to protocol are needed, 4) identify unexpectedly high dropout rates that threaten the trial’s ability to produce credible results, 5) ensure the credibility of the study, 6) ensure the validity of study results, and most importantly, 7) protect the safety of trial participants. The safety review committee will meet quarterly. If irregularities are identified in any of the goal areas listed above, the committee will propose changes to the protocol or study infrastructure in order to remedy the problem. In the event of a severe problem, the committee may advise termination of the study.

Potential Problems and Pitfalls

There are several potential pitfalls that may affect this study. However, if these are anticipated and managed appropriately, we believe they will not significantly impact the validity of the findings.

We have been conservative with the estimate of the anticipated number of subjects during the funding period. There are typically only several patients at MUSC's GI clinic per month that present with dysplastic Barrett's (or Barrett's with IMC) who are naïve to treatment. Therefore, we are proposing a pilot study with a conservative initial enrollment goal of 20 patients. This number can be increased to compensate for subjects who are potentially withdrawn or LTFU. If this pilot study proves to be informative, a multicenter initiative would be the next step.

Another challenge will be ensuring subject compliance with both PPI and liquid alginate therapy. This is particularly salient in patients who experience improvement in symptoms, and feel that they don't need to take medicine anymore, especially since the recommended dose of the study drug will be four times a day. We will contact the patients in between each 2-3 month visit, via telephone call and routinely reiterate the importance of medication compliance. We will also accurately record adherence, as mentioned above, by asking patients to bring in all bottles (used and unused) that were dispensed to them. Moreover, in the cases that prompted this line of research, we observed benefit associated with only twice daily dosing of alginate, making it feasible that our hypotheses could be met even if half the recommended dose is taken.

Lastly, the small sample size will limit the validity and generalizability of our observations. The numbers may be further be limited as patients undergoing RFA and cryotherapy will be analyzed separately. As mentioned above, this is intended to be a hypothesis-generating study that may inform the design of a larger multi-center initiative.

References

2. Boni, L., A. Benevento, S. M. Shimi, and A. Cuschieri. "Free Radical Production in the Esophago-gastro-duodenal Mucosa in Response to Acid and Bile." *Diseases of the Esophagus Dis Esophagus* 19.2 (2006): 99-104. Web.
3. Castell, Donald O., Christine Boag Dalton, David Becker, Jane Sinclair, and June A. Castell. "Alginic Acid Decreases Postprandial Upright Gastroesophageal Reflux." *Digest Dis Sci Digestive Diseases and Sciences* 37.4 (1992): 589-93. Web.
4. Chiu, C.-T., C.-M. Hsu, C.-C. Wang, J.-J. Chang, C.-M. Sung, C.-J. Lin, L.-W. Chen, M.-Y. Su, and T.-H. Chen. "Randomised Clinical Trial: Sodium Alginate Oral Suspension Is Non-inferior to Omeprazole in the Treatment of Patients with Non-erosive Gastroesophageal Disease." *Alimentary Pharmacology & Therapeutics Aliment Pharmacol Ther* 38.9 (2013): 1054-064. Web.

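### Read literally, the control definition depends on therapy over the whole treatment course, so it can leave out poor responders; the plan sets no time point and no rule for changed therapy

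*Combined protocol and SAP*

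**What the plan says.** Study Design: "The control group will be a historical cohort of Barrett's esophagus patients treated in the last 5 years by the same endoscopists using similar approaches". The same sentence goes on: "these are patients who were prescribed twice daily PPI therapy alone during treatment". No date is attached to the PPI condition. There is no eligibility list for controls, and nothing is said about a control whose medication changed during treatment.

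Sample Size Calculation and Statistical Consideration: "The historical data maintained by the PI have n= 32 patients treated under similar conditions". The number screened or excluded to reach 32 is not given. The only censoring described is for patients without complete response when the study ends.

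Enrollment: alginate patients are recruited once ablation has been decided on, and they start the study drug on the day of the first procedure. The section adds: "If patients are on concurrent H2 blocker therapy, this will be stopped after enrollment in the study".

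Background: "A recent case study by the current authors demonstrated initial failed response of BE with HGD to RFA and subsequently cryotherapy". In that patient alginate was added afterwards, and the response followed.

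Monitoring: "Subjects may be withdrawn from the study if they are lost to follow up, or if they endorse lack of compliance" with the study drug or the PPI.

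**The concern.** One cohort is fixed before treatment. The other, on the plain wording, is fixed by a condition that can be confirmed only once treatment has ended. If a control's therapy was changed because ablation was failing, that patient was not on PPI alone throughout and falls outside the definition because of a poor response. The Background case shows that this path exists for this group's patients.

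Specific Aim 1, the primary aim, compares one-year eradication with these controls. Losing poor responders would raise the control rate and shorten control time to CRIM, which would understate any benefit of alginate. Matching on therapy type and Barrett's length, and stratifying by grade and treatment, cannot correct selection on something that happens after baseline. The planned confidence interval for the rate difference would not show this bias either.

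**Working it through.** The plan has no figure to reproduce: it disclaims a power calculation, and its two sample sizes reflect who is available. The check is how far the control estimates could move under the plan's own model.

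**Inputs from the Sample Size section**
- 32 controls and about 20 alginate patients.
- Exponential time to complete response, with a median of about 22 months under current treatment and below 18 months as the example of sufficient improvement.

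**Assumptions not in the documents**
- Follow-up of 24 months.
- *k* = 1, 2 or 4 affected patients.
- None of them reaches CRIM within 24 months.

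**Step 1: one-year rates.** Rate = ln 2 / median; one-year CRIM = 1 − exp(−12 × rate).
- 22 months: 0.6931/22 = 0.03151 per month, giving 31.5%.
- 18 months: 0.6931/18 = 0.03851 per month, giving 37.0%.
- Gap: 5.5 points.

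**Step 2: expected control data.**
- CRIM by one year: 32 × 0.3148 = 10.07.
- CRIM by 24 months: 32 × 0.5305 = 16.98.
- Person-time: 16.98/0.03151 = 538.8 months.

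**Step 3: effect of the selection, seen two ways.**
- (a) The 32 are those who remain, and *k* patients are added back: one-year CRIM = 10.07/(32 + k); rate = 16.98/(538.8 + 24k).
- (b) The full set is 32, and *k* patients are dropped: one-year CRIM = 10.07/(32 − k); rate = 16.98/(538.8 − 24k).

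| k | (a) one-year CRIM | (a) median, months | (b) one-year CRIM | (b) median, months |
|---|---|---|---|---|
| 0 | 31.5% | 22.0 | 31.5% | 22.0 |
| 1 | 30.5% (−1.0) | 23.0 | 32.5% (+1.0) | 21.0 |
| 2 | 29.6% (−1.9) | 24.0 | 33.6% (+2.1) | 20.0 |
| 4 | 28.0% (−3.5) | 25.9 | 36.0% (+4.5) | 18.1 |

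Under (a) the listed controls show 31.5% and the true figure is lower. Under (b) the true figure is 31.5% and the listed controls show more. Either way the controls look better than they should. In (b) with *k* = 4, the 5.5-point gap shrinks to 37.0 − 36.0 = 1.0 point.

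**Step 4: sampling error for comparison.**
- Expected events: 16.98 in controls and 20 × 0.6031 = 12.06 with alginate.
- Standard error of the rate difference: √(0.03151²/16.98 + 0.03851²/12.06) = 0.01347.
- 95% interval: 0.0070 ± 1.96 × 0.01347, or −0.019 to 0.033 per month.
- At *k* = 4 the control rate moves by 0.03151 − 0.02674 = 0.0048 in (a) and 0.03834 − 0.03151 = 0.0068 in (b). Both are well inside the half-width of 0.026.

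**The case against.** The best defence is that the sentence describes usual care and is not a selection rule. It follows a dash, the verb is prescribed, and the starting prescription may be all that is meant. Elsewhere, PPI alone is simply the contrast to PPI plus alginate. The Sample Size section describes the 32 by shared facility and physicians and reports no filter on regimen. This stands as far as it goes: the benign reading is possible. It does not close the point, because someone abstracting charts could apply either reading and the protocol does not choose.

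Some stronger inferences are tempting and should not be drawn:

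- *Poor responders have been removed from the 32.* No section says so. The Background gives one case, and the documents do not place it in the 5-year window or in the investigator's data. Potential Problems and Pitfalls mentions further experience ("in the cases that prompted this line of research, we observed benefit associated with only twice daily dosing of alginate"), but says nothing about earlier failure or when alginate was started. The Safety section notes that the product is not sold in the US, so frequent past escalation to it cannot be presumed.
- *The comparison is biased toward controls overall.* Monitoring allows alginate patients to be withdrawn after enrollment, and Potential Problems and Pitfalls allows extra enrollment to compensate. Both cohorts can lose patients after baseline.
- *Past H2-blocker users are shut out as controls.* The word alone may only mean without alginate. If they are excluded, both cohorts are treated without an H2 blocker, since it is stopped in the alginate cohort. Adding such controls would be a trade-off.
- *The distortion is 7 to 12 points.* That follows from assuming 19 of 32 controls in remission (59.4%) and 4 or 8 patients left out (19/36 = 52.8%; 19/40 = 47.5%). The documents supply none of these numbers, and the plan's own median gives 31.5%.

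It is also fair that comparisons are descriptive and that the plan's 18-month example is set against a cited 22-month figure, not against these 32 patients. That limits the consequence, but the primary aim still rests on the controls.

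**Conclusion.** The point holds as a defect of definition. As written, the control condition can be read as depending on events after baseline, and nothing in the plan says what happens to a control whose therapy was changed. Applied literally, it can remove poor responders from the primary comparison and flatter the control one-year rate and time to CRIM.

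The size is unknown because the number affected is unknown. On the plan's 22-month exponential median, with 24 months of follow-up and no CRIM among the affected patients, the shift is about 1 to 2 points for one or two patients and 3.5 to 4.5 points for four. Sampling error is larger than any of these. A reader might conclude that the control estimate is already biased, or that the study will miss a benefit; the documents establish neither, and the net direction stays open. The change is worth making because it is cheap and because the results are meant to inform a randomized trial.

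**What to change.** - Define controls by the regimen prescribed at the first treatment session. Include all consecutive patients in the 5-year window who meet that definition and the study's baseline criteria, and keep them whatever was added later.
- Primary outcome: count CRIM reached after alginate was added as not reached on PPI alone at one year. This assigns an outcome and can tilt toward alginate, so state how many controls it affects.
- Time to CRIM: show results both censored at the switch and with follow-up continued. Censoring assumes that switched patients would have fared like the rest, which is doubtful after a poor response; continuing follow-up mixes in any effect of the added therapy.
- Report the numbers screened, excluded and escalated.
- Tabulate baseline H2-blocker use in both cohorts, without requiring that such users be added as controls.

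The cost is a re-screen of the centre's own charts and a short change of wording. The resulting control set may differ from the 32 now listed.

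### The exclusion criteria are stated for alginate patients only and not for the 32 historical controls, so the cohort difference mixes any alginate effect with patient selection of unknown direction and size

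*Combined protocol and SAP*

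**What the plan says.** All places are in the combined protocol and SAP.

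- **Eligibility Criteria, exclusions.** The list includes "Moderate to severe renal impairment, as defined by eGFR < 60 for 2 consecutive readings", "Patients with uncontrolled hypertension or decompensated heart failure" and "Patients with elevated calcium or potassium on screening laboratory testing". Lack of decision-making capacity, hydroxybenzoate allergy and pregnancy complete it. The section opens by describing who may be enrolled.
- **Enrollment.** The next section confirms whom the criteria address: "Eligible patients who provide informed consent will be included in this prospective study".
- **Study Design.** Controls are defined separately: "The control group will be a historical cohort of Barrett's esophagus patients treated in the last 5 years by the same endoscopists", with similar approaches and twice-daily PPI alone. No eligibility criterion is attached.
- **Hypotheses & Specific Aims, SA 1.** "Patients will be matched by type of therapy, and to the best of our ability, length of Barrett's".
- **Sample Size Calculation and Statistical Consideration.** The historical data hold "n= 32 patients treated under similar conditions (e.g. facility, physicians"). Disease grade and treatment type are given as examples of stratification covariates. The section plans an exponential rate for each cohort and the rate difference with a 95% confidence interval. It states that comparisons are descriptive and that no hypothesis test will be done.

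**The concern.** With a historical comparator, the two groups should at least be drawn from patients who could have been in either. Here one group has passed a set of medical filters and the plan does not pass the other through them. A past patient with an eGFR below 60 or decompensated heart failure could not have entered the alginate cohort but can sit among the 32 controls. If such patients clear Barrett's epithelium at a different speed, for whatever reason, the difference in one-year CRIM (the primary outcome) and the rate difference will carry that gap along with any effect of alginate. Matching on therapy and segment length does not remove it.

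What is at stake is the pilot's between-cohort estimate, an obvious input when a later randomised trial is planned. The confidence interval around it expresses random error only and does not cover selection.

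**Working it through.** The plan gives no figure for this bias, so there is nothing to reproduce. The check asks how far the control median could move if excludable controls were removed.

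**Inputs from the Sample Size section.** About 20 alginate patients; 32 controls; exponential time to CR; published median under current treatment of about 22 months. The plan reports no median for its own 32 controls, so 22 months stands in for it here.

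**Assumed inputs, absent from the documents.** f = share of controls who meet an exclusion. r = their eradication rate relative to the other controls.

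**Step 1, the exponential model.** Rate = ln 2 / median = 0.6931 / 22 = 0.0315 per month. One-year CRIM = 1 − exp(−12 × 0.0315) = 31.5%.

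**Step 2, the mixture.** Let λ be the rate in controls who pass. Fix the median of all controls at 22 months and solve

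(1 − f) exp(−22λ) + f exp(−22rλ) = 0.5

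The median of controls who pass is ln 2 / λ. For f = 0.20 and r = 0.75, λ = 0.0333: 0.8 × 0.480 + 0.2 × 0.577 = 0.50, so the median is 20.8 months. Other values (months):

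| r | f = 10% | f = 20% | f = 30% |
|---|---|---|---|
| 0.25 | 19.9 | 17.7 | 15.7 |
| 0.5 | 20.7 | 19.4 | 18.2 |
| 0.75 | 21.4 | 20.8 | 20.2 |
| 0.9 | 21.8 | 21.5 | 21.3 |
| 1.25 | 22.5 | 23.0 | 23.6 |

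The last row shows that the shift reverses if excludable controls clear faster.

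**Step 3, the same case on the primary outcome.** For f = 20% and r = 0.75, one-year CRIM is 32.9% in controls who pass and 31.5% in all controls, a gap of 1.4 points with no drug effect.

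**Step 4, random error.**

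- Rate ratio, if every patient reached CR (the best case): SE of the log ratio = √(1/20 + 1/32) = 0.285. The 95% limits lie a factor of exp(1.96 × 0.285) = 1.75 either side of the estimate. The illustrative bias is a ratio of 22 / 20.8 = 1.06.
- One-year CRIM difference, with all statuses known: 1.96 × √(0.329 × 0.671 / 20 + 0.315 × 0.685 / 32) = 0.26, or about 26 points either way, against 1.4 points.

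**The case against.** **The plan is silent; it does not refuse.** No section says that controls are exempt from the criteria, and facility and physicians are only examples of similar conditions. This stands as far as it goes: it cannot be asserted that the controls were unscreened. But the plan as written does not apply the criteria to them, and an analyst following it would keep all 32, subject only to matching.

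**The direction is not known.** A reader might infer that a healthier alginate cohort is set against sicker controls whose slower treatment would pass for an alginate benefit. The documents do not support that. Most exclusions concern product safety or consent, and the Safety section ties several of them to the product's contents. The Endoscopic treatment section names Barrett's length and hiatal hernia as determinants of the number of sessions, and no section links renal, cardiac or electrolyte status to eradication speed. Controls were also, by definition, well enough to be treated. The same silence covers the criterion of more than 3 cm. Shorter-segment controls, if kept, would tend to work against alginate, although matching on length partly deals with this. This objection stands in full.

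**The go-ahead signal does not use these controls.** A reader might also set the bias against the improvement from 22 to 18 months. That benchmark is the wrong one. The plan places the alginate cohort's own median beside a published 22 months, and filtering the controls changes neither. This stands. What the selection affects is the rate difference and the one-year CRIM comparison.

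**The study is descriptive and small.** The Potential Problems section calls it hypothesis-generating and concedes limited validity. This lowers the consequence but does not remove it, because the plan still reports a between-cohort difference with an interval.

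**Conclusion.** The point holds as a gap in how the comparator is defined. Eligibility is stated for enrolled patients only, it is not carried over to the 32 controls, and comorbidity is neither matched on nor named as a stratum. The between-cohort estimates therefore mix any alginate effect with selection.

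Neither direction nor size can be read from the documents. In the illustrative case (20% excludable, 0.75 times the rate) the control median moves by 1.2 months (22 to 20.8), well inside the random error. A marked effect, such as 30% at half the rate, would move it to 18.2 months, but nothing in the documents supports that value over a null or reversed one. All of these figures rest on the assumed f and r, on exponential times, and on 22 months standing in for the unreported control median. The point is worth correcting because the remedy is cheap and works whichever way the bias runs. It is not evidence that the comparison favours alginate.

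**What to change.** Add to the Study Design and Sample Size sections that:

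- every inclusion and exclusion criterion that can be read from the chart is applied to the controls as of the date of first treatment;
- controls with a missing value are kept and their number is reported, because two consecutive eGFR readings, recent calcium and potassium, or a capacity judgement may be absent from past records, and availability of data should not decide who stays;
- the number of the 32 failing each criterion is reported;
- one-year CRIM and the rate difference are presented both for controls who pass and for all 32.

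The same wording covers the segment-length criterion.

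The cost is a review of 32 records, some missing laboratory values and a somewhat smaller comparator. If 20% failed (0.20 × 32 = 6.4, so about 26 remain), the best-case limits for the rate ratio would widen from a factor of 1.75 to exp(1.96 × √(1/20 + 1/26)) = 1.79. The all-controls result is kept, so nothing already planned is lost, and no patient's treatment changes.
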